3.3 Statistical process control to study time to effect

Cumulative sum chart (CUSUM) procedures will be used to monitor for changes in each of the outcome variables throughout the intervention period. The CUSUMs will be based on logistic regression models estimated from the baseline data (Steiner et al, 2000). An overall CUSUM plot, risk-adjusted for region, facility level, and whether a facility was part of SBBC phase I or not will be

constructed. In addition, separate plots will be constructed per region, facility level, and SBBC-I (yes/no), as we anticipate substantial differences both in baseline levels and intervention effects between the levels of these factors. The signal limit for the CUSUM will be set according to a probability of 5% of getting a false alarm during 100 000 births in case there is no change from the baseline.

3.4 Exploration of contextual and implementation fidelity predictors of outcome trends during the intervention period

To explore facility-level factors predicting change in clinical outcomes during the intervention period, we will analyze monthly aggregated data from each facility using mixed effects Poisson regression. Random effects will be used to model dependency in data from the same facility. Development of outcome rates during the intervention period will be modelled non-linearly using splines and accounting for the number of births in each facility in each month. Candidate time-fixed predictor variables are region, facility level, average no. of births per month in the baseline period, baseline levels of outcomes, staff density, and readiness level. Effects of these will be assessed by interaction terms between the variable and the splines functions of intervention month. Effects of time-varying predictors like degree of uptake of new routines (use of Moyo and NeoBeat), and (cumulative) amount of training and mentorship involvement will be assessed by their rate ratios, assuming lagged (by one month) effects of training and mentorship involvement.

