Adjustments will be made for monthly rates of referrals-in, births with not heard/detected FHR, and preterm births for each facility. Since these, as well as data regarding use of Moyo and NeoBeat, are only available for a substantial proportion of births from August 2024 and onwards, adjusted results and results for the latter predictor variables will be presented for the period August 2024 to December 2025. Unadjusted results, and results adjusted for BW, mother's age, and multiples, will be presented for the whole intervention period whenever possible.

In these analyses, the 30 SBBC-I facilities and the 122 new facilities will be analyzed separately.

4 Reporting and multiplicity considerations

Due to the non-randomized pre-post design of the study no causal claims will be made based on the estimated effects/associations.

All estimates will be presented with 95% confidence intervals (CI) and corresponding p-values from significance tests. For the estimates of overall efficacy for the two co-primary outcomes, p-values <0.025 will be considered statistically significant. All other p-values will be interpreted as exploratory.

If a confidence interval goes beyond the region of possible values for the parameter, we will report the interval truncated to possible values.

5 Graphical displays of results

Results from the main analyses will be supplemented with prediction plots based on the final models.

Furthermore, to accompany the CUSUM plots and illustrate the impact of the intervention over time, variable life adjusted displays (VLAD) will be made (Lovegrove, 1997). These plots will be made by aggregating the difference between the estimated conditional probability for fatal outcome based on a model estimated from baseline data, and the observed outcome, and can thus be interpreted in terms of estimated numbers of lives saved. The same logistic regression models as used for the CUSUM plots described in Section 3.3 will be used to estimate the probability of fatal outcome under baseline conditions.

For the promotor/inhibitor analyses, estimated marginal rates will be presented over time for each considered factor, based on the Poisson regression models.

6 Missing data and sensitivity analyses

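### The VLAD's lives-saved reading conflicts with the SAP's bar on causal claims, and no uncertainty band is specified for the curve

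*SAP*

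**What the plan says.** Section 4 of the SAP (Reporting and multiplicity considerations) notes the non-randomised pre-post design and concludes that "no causal claims will be made based on the estimated effects/associations". It then sets a general reporting rule: "All estimates will be presented with 95% confidence intervals (CI) and corresponding p-values from significance tests".

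Section 5 (Graphical displays of results) introduces the VLAD with the purpose "to accompany the CUSUM plots and illustrate the impact of the intervention over time, variable life adjusted displays (VLAD) will be made". The curve accumulates, birth by birth, the predicted probability of death from a baseline model minus the observed outcome. Section 5 says that it "can thus be interpreted in terms of estimated numbers of lives saved".

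On the model behind the curve, Section 5 says: "The same logistic regression models as used for the CUSUM plots described in Section 3.3 will be used". Section 3.3 describes the overall version as "risk-adjusted for region, facility level, and whether a facility was part of SBBC phase I or not". It lists no individual-level covariates, no facility effects and no time trend. The only error control there belongs to the CUSUM, whose signal limit is set for a "probability of 5% of getting a false alarm during 100 000 births in case there is no change from the baseline".

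Section 7 states that under-reporting of deaths in the retrospective baseline of the new sites is believed to be substantial. It plans a comparison of the two baseline sources to inform discussion of the main analyses. It does not mention the VLAD.

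**The concern.** A count of lives saved is the number of deaths that would have happened without the intervention and did not. That is a causal quantity. Section 5 derives this reading from how the plot is built, although the plot only compares observed deaths with deaths predicted at baseline rates. The difference can also contain changes in reporting, case-mix, secular trend and chance, which is the reason for the rule in Section 4.

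The second issue is uncertainty. The baseline model is estimated once and applied to every intervention birth. If its predicted rate is slightly off, the error has the same sign at each birth and grows in proportion to the number of births, whereas chance variation in observed deaths grows only with the square root. A long, smooth drift can therefore arise without any change in mortality. A reader shown the curve without a band cannot tell such a drift from a benefit or a harm.

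**Working it through.** The SAP states no event rate, death count or lives-saved figure, so there is no planned figure to reproduce. The check is illustrative.

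**Inputs from the SAP.** Baseline data run from 2023 into early 2024, the intervention started April-June 2024, and data collection ends at the close of 2025. Counting from January 2023 gives 36 months in all, for example 16 baseline and 20 intervention months for a start at the beginning of May.

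**Assumptions.** D = 100, 200 or 400 baseline deaths, constant birth volume, independent births, no true change, and one common rate in place of the adjusted model. The main illustration uses 16 baseline and 19 intervention months; other splits follow.

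**Formulas.** Expected deaths: E = D × 19/16. The final VLAD is expected minus observed.
- Chance variance of observed deaths: E.
- Variance from estimating the baseline rate: (19/16)² × D = E²/D.
- 95% limits: ±1.96 × √(E + E²/D).

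**Results, 16 and 19 months.**

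| D | E | E²/D | Both sources | Poisson only, 1.96√E |
|---|---|---|---|---|
| 100 | 118.75 | 141.0 | ±31.6 | ±21.4 |
| 200 | 237.5 | 282.0 | ±44.7 | ±30.2 |
| 400 | 475 | 564.1 | ±63.2 | ±42.7 |

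Baseline error is the larger component. A band that ignored it would be √(16/35) = 0.68 of the right width, about one third too narrow.

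**Other splits, same formulas, for D = 100, 200 and 400.**
- 16 and 20 months: ±32.9, ±46.5, ±65.7.
- 15 and 21 months (start of April): ±35.9, ±50.8, ±71.9.
- 17 and 19 months (start of June): ±30.2, ±42.6, ±60.3.

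The choice of split changes little.

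**Check on a births scale.** Assume 100 000 births in each period and a 1% risk.
- Chance variance is 100 000 × 0.01 × 0.99 = 990, and baseline-estimation variance is the same.
- The limits are 1.96 × √1980 = ±87.
- In simulation, 26% of no-change curves ended more than 50 deaths from zero (11% at a 0.5% risk, 35% at 1.5%).

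**Clustering.** At an assumed design effect of 2, the limits widen by √2: ±31.6 becomes ±44.7 and ±63.2 becomes ±89.3. Stable differences between facilities partly cancel between periods. What widens the band is variation over time in facility rates or in shares of births, and the SAP gives no figure for either.

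**Direction of the reporting bias.** If the baseline misses a share u of deaths and the intervention period misses none, the no-change curve ends at -N × p × u. With N = 100 000 and p = 1%, u = 10%, 20% or 30% gives -100, -200 or -300. These shares are assumptions applied to the whole baseline. Under-reporting confined to the new sites' retrospective data would shift the overall curve less.

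**The case against.** The strongest defence is that the VLAD is a supplementary display. The efficacy result is the marginal relative risk of Section 3.2, with a confidence interval and a 0.025 threshold, and no decision rests on the VLAD. Section 5 says only that the curve can be read as an estimated count. The SAP uses effect language elsewhere under the same disclaimer, and the plot could be published with that caveat. This stands as a limit on severity. It does not remove the conflict in wording.

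Several stronger readings are tempting but unsupported:
- A reader might infer that the plan leaves the VLAD without any uncertainty statement. The Section 4 rule on intervals covers all estimates, and Section 5 calls the count estimated, so the rule can be read to apply. The gap is that Section 5 does not apply it to a cumulative curve or say how.
- A reader might infer that chance is bound to be shown as deaths averted. It can be, but the CUSUM beside the VLAD offers a formal check on chance. That check neither puts a band on the VLAD nor covers baseline-estimation error.
- A reader might infer that baseline error flatters the intervention. Sampling error can go either way, and the under-reporting that the SAP describes works against the intervention.
- A reader might infer that maternal death is worst affected. With fewer deaths the limits are narrower in absolute terms (±32 at D = 100, ±63 at D = 400). They are wider only relative to expected deaths: 31.6/118.75 = 27% against 63.2/475 = 13%.

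**Conclusion.** The concern holds as a conflict of wording together with a gap in specification. Calling the VLAD a picture of the intervention's impact and a count of lives saved goes beyond what Section 4 allows. No method is given for an interval on the curve, and nothing brings baseline-model error or clustering into it.

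Under the stated assumptions, a final value some 30 to 65 deaths from zero is compatible with no change, and further out with clustering or larger death counts. These sizes rest on assumed death counts, constant volume and independent births, and should be replaced by the trial's own. Separately, under-reporting at the new sites would pull the curve towards apparent excess deaths by an amount that the SAP does not let one estimate.

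A reader might infer that Sections 4 and 5 cannot both be followed, or that the primary result is compromised. Neither follows: the plot can be kept with neutral labelling, and the primary analysis is untouched. A change is worth making because the figure yields a single, easily quoted number.

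**What to change.** In Section 5:
- Describe the VLAD as the cumulative difference between deaths expected under the baseline model and deaths observed. Label the axis accordingly, and remove the lives-saved and impact-of-the-intervention wording.
- Draw each VLAD with a 95% no-change band centred on zero that includes baseline-model uncertainty and facility clustering. One option is a bootstrap of whole facilities, keeping each facility's baseline and intervention births together and refitting the baseline model each time.
- State that movement inside the band is not evidence of benefit or harm.
- Note that under-reported baseline deaths at the new sites shift the curve towards apparent excess deaths.

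This needs no new data and leaves the primary analysis unchanged. The cost is a few sentences of SAP text, one resampling run per plot and a less striking supplementary figure.
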